#### *16.4.1.11 Supportive Analyses*

The list of supportive analyses will be presented in the SAP. The list will include the same analysis performed on the per protocol set of subjects and on the modified intent-to-treat (mITT) population. Possibly, a rank ANCOVA on the ITT set of subjects will be conducted in case of major outliers. Major outliers are defined as observations associated with an absolute studentized residual above 5. The last supportive analysis is the primary analysis with the following covariates added to the model: the duration of vision loss at baseline of the second affected/not yet affected eye, the baseline GCL volume, the region, the region-by-treatment interaction.

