3.2. Sample size consideration

Sample size calculation is based on the primary endpoint which is the change from baseline to 1.5 years post-treatment of the visual acuity (LogMAR BCVA). Masked preliminary data of the Phase III RESCUE and REVERSE sham-controlled studies of GS010 and monitored data from the Phase I/IIa safety and tolerability study of GS010 are used to estimate the standard deviation of the change from baseline to each available visit. These data do not take into account a potential treatment effect in the RESCUE and REVERSE studies and if there is an effect, the standard deviation may be overestimated.

From this masked preliminary analysis, a standard deviation of 0.55 LogMAR has been estimated for the LogMAR change from baseline; this is reduced to 0.50 with the inclusion of baseline LogMAR as a covariate. Using this reduced value for Standard Deviation (SD) and a treatment effect of 0.3 LogMAR in the change from baseline, the requested sample size to reach a power of 80% ($\alpha = 0.05$ two-sided) according to a classical Analysis of Covariance (ANCOVA) model including the baseline LogMAR value as covariate has been estimated using SAS PROC POWER to be 45 evaluable subjects per treatment group (i.e. 90 subjects in total). Depending on the number of subjects who terminate early, additional subjects may be enrolled through the end of the recruitment period.

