13.1.4. Primary analysis of primary efficacy variable(s)

The primary analysis will be performed on the ITT population on the planned treatment (as randomized). The primary endpoint is the change from baseline of the BCVA, reported in LogMAR at 1.5 years post-treatment. Descriptive statistics will be presented for the baseline and 1.5 years post-treatment timepoints as well as for the change from baseline to the 1.5 years post-treatment based on data after imputation.

The treatment difference will be assessed with an ANCOVA model which includes terms to adjust for the baseline LogMAR value and includes treatment group as a fixed effect.

The analysis will be performed using a significance level of 0.05 (two-sided).

SAS code:

ARM =subject Treatment arm; change=Logmar change from baseline of second-affected/not-yet-affected eyes; Logmar0=Logmar at baseline

```
proc mixed data=XXX_;
class ARM;
model change=ARM logmar0 /s CL;
estimate " GS010 arm vs Placebo arm" ARM -1 1;
run;
```

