13.1.5. Supportive analysis of primary efficacy variable(s)

Shift table and Mac Nemar test between Eyes on-chart/off-chart for LogMAR BCVA at baseline and Eyes on-chart/off-chart for LogMAR BCVA at 1.5 years by arm will be performed.

The primary analysis with the same model will be repeated for the following:

1. Using the mITT population, if different from the ITT population
2. Using the PP population
3. Same analyses will be conducted on the LogMAR instead of the change of LogMAR (analyses will be not adjusted on LogMAR at baseline but with duration from vision loss)

Using a model at the subject level, with repeated values for eye. We need to have comparison between treatment group (GS010 vs Placebo) and comparison between GS010 eye in GS010/ GS010 ARM and GS010 eye in GS010/ Placebo ARM.SAS code:

ID=identifiant; TREAT =(Placebo in GS010/ Placebo ARM / GS010 in GS010/ Placebo ARM / GS010 first affected eye in GS010/ GS010 ARM / GS010 second affected eye in GS010/ GS010 ARM ; change=Logmar change from baseline; Logmar0=Logmar at baseline;

```
proc mixed data=XXX ;
class ID TREAT (ref="PLACEBO") ;
model change= TREAT logmar0 /s CL;
random intercept/sub=ID type=AR(1);
lsestimate TREAT " GS010 vs Placebo " 1 1 1 -3/cl divisor=3;
lsestimate TREAT " GS010 in GS010/GS010 ARM vs GS010 in GS010/Placebo ARM" -2
1 1 0/cl divisor=2;
run;
```

4. Primary ITT analysis adjusted on potential confusion factors:

ANCOVA will be used to analyze the effect of treatment on the change from baseline of the BCVA, reported in LogMAR at 1.5 years post-treatment adjusted on baseline LogMAR value, and potential confusion factors. A backward selection approach will be considered to keep significant covariates among: Gender, Age at onset of the disease, Duration of vision loss, Pediatrics/Adults, Previous Idebenone treatment, BCVA at baseline as a continuous parameter, BCVA on-chart/off-chart at baseline, BCVA on-chart/off-chart at nadir, LogCS at baseline as a continuous parameter, LogCS on-chart/off-chart at baseline, LogCS on-chart/off-chart at nadir, baseline GCL volume, baseline Quadrant Temporal RNFL, baseline PMB RNFL and Region. We will consider a p-value of <0.2 in univariate model (adjusted on logMAR at baseline) for entry in the multivariate model and a p-value of >0.05 for removal from multivariate model. If a covariable has a p-value>0.05 but

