causes a strong variation in the estimates of the treatment (+/-20%), then it will be conserved in the model and considered as a confounding factor. If linear hypothesis between change from baseline and quantitative variable is not verified, thus quantitative variable should be included in the model as qualitative variable (on the covariate's quartiles for example). Multicollinearity of independent variables (those which enter in the multivariate model) was checked via the variance inflation factor (VIF) statistic. If $VIF > 10$ between two or several covariables, only one covariable should be included in the model.

SAS code:

ARM =subject Treatment arm; change=Logmar change from baseline of second-affected/not-yet-affected eyes; Logmar0=Logmar at baseline; VARi=quantitative covariables i; VARCi=qualitative covariables i

Univariate analysis for quantitative variable:

```
proc mixed data=XXX;
model change= logmar0 VARi/s CL;
run;
```

Univariate analysis for qualitative variable:

```
proc mixed data=XXX;
class VARCi;
model change= logmar0 VARCi /s CL;
lsmeans VARCi;
run;
```

Multivariate analysis:

```
proc mixed data=XXX;
class ARM VARC1 VARC2 ...;
model change=ARM logmar0 VARC1 VARC2... VAR1 VAR2 .../s CL;
run;
```

Test of multicollinearity:

```
proc reg data= XXX;
model change= ARM logmar0 COUNTRY VAR1 VAR2 VAR3 /VIF TOL COLLIN;
run;
```

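### The supportive covariate-adjusted ITT analysis selects covariates by p-value, which makes its treatment test modestly anti-conservative, and its 20% retention rule lets the fitted model depend on the treatment estimate.

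*SAP*

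**What the plan says.** Protocol 16.4.1.11 ends its supportive analyses with the primary model plus a named set of covariates: "the duration of vision loss at baseline of the second affected/not yet affected eye, the baseline GCL volume, the region", and the region-by-treatment interaction. The same section leaves the full list of supportive analyses to the SAP.

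SAP 13.1.5, item 4, does not use that set. It states: "A backward selection approach will be considered to keep significant covariates among" fifteen named terms. A term enters the multivariable model at p<0.2 in a model that also contains baseline LogMAR (the sample code for this step omits the arm), and leaves at p>0.05. The exception is that if a non-significant covariate "causes a strong variation in the estimates of the treatment (+/-20%), then it will be conserved in the model". The final PROC MIXED call gives default confidence limits, and nothing allows for the selection. Three choices are left open: which model the 20% is measured against, how a non-linear covariate is recoded (quartiles are offered as an example), and which of several collinear covariates is dropped.

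SAP 3.4 records a change to the supportive analyses in 13.1.5 and gives no reason for moving from a fixed list to selection. SAP 13.1.4 fixes the primary model as arm plus baseline LogMAR, and SAP 6.3 assigns all type I error to it.

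**The concern.** Two separate features need attention.

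- **Selection by p-value.** The covariates are chosen on the same outcome data that then test the treatment. The final standard error treats the chosen model as if it had been fixed in advance, so it tends to be too small.
- **A threshold relative to the treatment estimate.** Twenty per cent of a large estimate is a large shift; twenty per cent of an estimate near zero is a trivial one. When the estimate is small, chance imbalance in a weak covariate is enough to keep it in.

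Item 4 is the SAP's multi-covariate adjustment of the primary ITT result. It yields a treatment estimate, interval and p-value that would be read beside the primary ones. At stake are the calibration of that p-value and interval, and whether the same model would be fitted in a null trial as in a positive one.

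**Working it through.** **Inputs.** SAP 3.2 puts the unadjusted SD of the change at 0.55 LogMAR and adds: "this is reduced to 0.50 with the inclusion of baseline LogMAR as a covariate". The difference to detect is 0.3 LogMAR, with 80% power, two-sided 0.05 and 45 per arm. SAP 13.1.5: 15 candidates. Baseline BCVA is already in the model, so 14 are open to selection. Two of those are on/off-chart status at nadir, which SAP 13.3 defines with post-treatment values. That leaves 12 baseline candidates.

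**The plan's own figure.** n per arm = 2(1.960+0.842)² × 0.50² / 0.30² = 43.6, so 44 by the normal approximation. The noncentral t gives 79.5% power at 44 and 80.4% at 45, which reproduces the stated 45.

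**Size of the 20% threshold.** SE of the treatment difference = 0.50 × √(2/45) = 0.105. At an estimate of 0.30 the threshold is 0.20 × 0.30 = 0.06. At 0.05 it is 0.20 × 0.05 = 0.01, about a tenth of the SE.

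**Why that matters (rough calculation, one standardised covariate).** Removing a covariate shifts the treatment estimate by about its coefficient times its imbalance between arms.

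- SE of the coefficient = 0.50/√90 = 0.0527. A covariate with p between 0.2 and 0.05 therefore has a coefficient between 1.28 × 0.0527 = 0.068 and 1.96 × 0.0527 = 0.103.
- SE of the imbalance = √(2/45) = 0.211.
- A shift of 0.06 needs an imbalance of 0.06/0.103/0.211 = 2.8 to 0.06/0.068/0.211 = 4.2 standard errors, which is rare.
- A shift of 0.01 needs 0.46 to 0.70 standard errors, which is commonplace.

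**Monte Carlo of the full rule, no treatment effect.** The runs use 45 per arm, residual SD 0.50 and complete data. Prognostic strength and correlation among candidates are assumptions; the documents give neither. The table shows the percentage of trials rejecting at 5%.

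| Candidates | Trials per cell | Residual variance explained | Full rule | Without 20% rule |
|---|---|---|---|---|
| 12 | 6,000 | 0 / 15 / 30% | 5.4 / 6.6 / 6.8 | |
| 12 (second run) | 6,000 | 0 / 15 / 30% | 5.5 / 6.5 / 6.3 | |
| 12 (third run) | 4,000 | range | 5.3-6.6 | 5.4-6.8 |
| 13 | 8,000 | none / weak / strong | 6.0 / 6.1 / 6.5 | 6.1 / 6.4 / 6.7 |
| 14 | 6,000 | 0 / 15 / 30% | 6.0 / 6.4 / 6.8 | |
| 14 (second run) | 6,000 | 0 / 15 / 30% | 5.4 / 6.6 / 6.9 | 5.4 / 6.9 / 7.1 |
| 14 (third run) | 14,000 | none / weak | 5.6-5.7 / 5.7 | 5.9 / 5.9 |

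The Monte Carlo SE is about 0.3 points at 6,000 to 8,000 trials and 0.2 at 14,000. With all candidates forced in, rejection was 4.8-5.3%. In the 13-candidate run the primary model had 80.2% power at a true 0.30 with no prognostic candidates, in line with the plan.

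Weak and strong in the 13-candidate run lie outside the 0-30% range. From the SD of the primary-model estimate, weak explains about 1 − (0.1073/0.1301)² = 32% of residual variance and strong about 1 − (0.1073/0.1912)² = 69%. Even there the full rule reaches only 6.5%.

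**Interval.** Coverage of the nominal 95% interval was 93.1-94.7% across the runs. In the strong case the mean reported SE was 0.1104 against an actual SD of 0.1147, so it was 3.7% too small (0.1104/0.1147 = 0.963).

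**Which rule causes what.** Removing the 20% rule leaves rejection the same or slightly higher (last column), so the excess comes from the p-value screen and backward removal. The 20% rule has a different effect, shown here as the percentage of trials keeping at least one covariate only because of it:

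| Run | True effect 0 | True effect 0.30 |
|---|---|---|
| 12 and 14 candidates | 41-63% | 3% (12 candidates, 15%) |
| 12 candidates, third run | 42-61% | 3% |
| 13 candidates | 44-60% | 4-7% |

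**The case against.** The strongest reply is about consequence. SAP 6.3 spends all alpha on the primary endpoint, the primary ANCOVA is fixed in advance, and item 4 stands beside mITT, PP, LogMAR-level and observed-data MMRM analyses. An excess of a point or two in one analysis without alpha cannot change the trial's decision. That stands, and it limits the weight of this point.

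The change is also disclosed. Protocol 16.4.1.11 defers to the SAP, and SAP 3.4 lists the change. That stands too: the criticism is of the method, not of concealment.

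The excess depends on assumed prognostic strength. With uninformative candidates some runs give 5.3-5.5%, which is within Monte Carlo error of 5%. This is fair, but candidates are listed because they are thought prognostic, and at 15-30% explained variance every run with those settings exceeds 6%.

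A reader might infer more than the material supports:

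- **That the 20% rule makes the p-value too small.** It does not; rejection is no lower without it.
- **That the inflation approaches 8%.** A run of 3,000 trials gave 7.7% at 30% explained variance, with 92.3% as the lowest coverage; none of the larger runs came near those values.
- **That the adjusted treatment estimate is biased.** With baseline-type candidates the simulated bias was at most 0.002 LogMAR. The nadir terms are a separate matter, because they include post-treatment values.
- **That item 4 was written with knowledge of the results.** SAP v10.0 postdates the 1.5-year analysis, but the documents do not show when item 4 was drafted.

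**Conclusion.** The point holds at modest size. Selecting covariates by p-value gives the item 4 treatment test a rejection rate of about 5.5-7% under no effect and interval coverage of about 93-94.5%, against about 5% rejection for a fixed set. The 20% rule adds no inflation, but about 40-60% of null trials keep at least one covariate only through it, against about 3-7% at a true 0.30 LogMAR. A check on the randomised result should not change its model according to that result.

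These figures assume complete data, single-degree-of-freedom candidates and explained variance of 0-30%, none of which the documents give. They leave out the analyst's freedom in the three open choices, which could raise the error further. The primary test and the sample size are unaffected.

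**What to change.** In SAP 13.1.5, item 4, delete the univariate screen, the backward removal and the 20% rule. Fit one ANCOVA with treatment, baseline LogMAR, and the baseline main effects of Protocol 16.4.1.11: duration of vision loss of the second eye, baseline GCL volume and region. Keep all terms whatever their p-values, and include no nadir terms. With the three regions of SAP 6.1 this uses 1+1+1+1+2 = 6 degrees of freedom plus the intercept, leaving 90 − 7 = 83 for error.

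Report the protocol's region-by-treatment interaction as a separate model. SAP 6.1 refers the effect of region on the treatment association to 13.1.5, where no interaction is now specified.

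Because SAP v10.0 postdates the 1.5-year analysis, use the protocol's list unchanged; a newly chosen set would raise its own doubts. A data-driven search for prognostic factors can stay if it is labelled descriptive and carries no treatment p-value.

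The cost is SAP wording and less programming than the present rule. The downside is that no data-driven search feeds the adjusted treatment estimate.

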13.1.6. Sensitivity analysis of primary efficacy variable(s)

Sensitivity analyses of the primary endpoint will be conducted only on observed data (data without imputed values) up to 1.5 years using a MMRM model with baseline adjustment; treatment group, study time points, and treatment group-by-time point interaction as fixed effects; and subjects as random effect.

SAS code:

ID=identifiant; ARM =subject Treatment arm (1=GS010 – 0=Placebo); change=change from baseline of second-affected/not-yet-affected eyes; Logmar0=Logmar at baseline; time=timepoint (time=0 is baseline)

```
proc mixed data=XXX;
where time>0;
class ID time ARM;
model change= time ARM ARM*time logmar0 /CL ddfm=KENWARDROGER;
```

```
repeated time/sub=ID type=AR(1);
lsmeans ARM*time/diff;
run;
```

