### 16.2 Sample Size

Sample size calculation is based on the primary endpoint which is the change from baseline to 1.5 years post-treatment of the visual acuity (LogMAR). Masked preliminary data of the Phase III RESCUE and REVERSE sham-controlled studies of GS010 and monitored data from the Phase I/IIa safety and tolerability study of GS010 are used to estimate the standard deviation of the change from baseline to each available visit. These data do not take into account a potential treatment effect in the RESCUE and REVERSE studies and if there is an effect the standard deviation may be over-estimated.

From this masked preliminary analysis, a SD of 0.55 LogMAR has been estimated for the LogMAR change from baseline; this is reduced to 0.50 with the inclusion of baseline LogMAR as a covariate. Using this reduced value for SD and a treatment effect of 0.3 LogMAR in the change from baseline, the requested sample size to reach a power of 80% ( $\alpha = 0.05$  two-sided) according to an ANCOVA model including the baseline LogMAR value as covariate has been estimated, using SAS PROC POWER, to be 45 evaluable subjects per treatment group (i.e. 90 subjects in total).

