13.2.3. Analysis of Secondary Efficacy Variables

Change in LogMAR BCVA analysis

Change in LogMAR compared to baseline, at each timepoint of the Follow-Up Period up to 5 years post- treatment will be analyzed at each visit using separate ANCOVA models as primary endpoint (see section 13.1.4).

Response status

For each response parameter and at each timepoint of the Follow-Up Period up to 5 years post- treatment, logistic model, including a factor for treatment group and the baseline value as a covariate will be considered on:

- Second-affected eye at timepoint (at eye level)
- First-affected eye at timepoint (at eye level)
- First and second affected eye at timepoint (at subject level): best response between both eyes

SAS code:

```
ARM=subject Treatment arm (1=GS010 – 0=Placebo); resp=responder variable; Logmar0=Logmar at baseline;
proc logistic data=XXX;
class ARM;
model resp=logmar0 ARM;
run;
```

For each of the response definitions and at each timepoint of the Follow-Up Period up to 5 years post- treatment, a logistic model, including a factor for treatment group, eye, the baseline value as a covariate, will be fit using GLMM for first and second affected eye at timepoint (at eye level)

SAS code:

```
ARM=subject Treatment arm (1=GS010 – 0=Placebo); resp=responder variable; Logmar0=Logmar at baseline;
proc glimmix data=XXX_ana;
class ID ARM;
model resp= ARM logmar0 /dist=bin solution cl;
random intercept/sub=ID type=ar(1);
run;
```

Parameters measured with SD-OCT, HVF and contrast sensitivity

The parameters detailed in sections 13.2.1 will be analyzed separately using a MMRM model, with adjustment for baseline score, as described in section 13.1.6.

Quality of Life assessments

Visual Functioning Questionnaire-25 (VFQ-25)

VFQ25 measures will be assessed at the subject level, looking at change from baseline for all subjects and comparing the change from baseline between the two arms (bilaterally treated subjects vs. unilaterally treated subjects).

Composite score and individual subscale scores from VFQ-25 will be summarized using descriptive statistics. Change from baseline at each visit for the composite score and individual subscales scores will be analyzed separately using a MMRM model, with adjustment for baseline score, as described in section 13.1.6.

36-Item Short Form Health Survey, Version 2 (SF-36v2)

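### The observed-data MMRM in SAP 13.1.6 fits one baseline slope to all visits, so at 1.5 years it can differ slightly from the primary ANCOVA even with nothing missing

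*SAP*

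**What the plan says.** SAP 13.1.4 analyses change at 1.5 years by ANCOVA with treatment and baseline LogMAR. Only one visit is in the model, so the baseline slope is the Week 78 slope. Missing values are first filled by clinical decision at data review and then by LOCF (SAP 13.1.3).

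SAP 13.1.6 gives the sensitivity analysis, an MMRM on observed values up to 1.5 years, with the model statement "model change= time ARM ARM*time logmar0 /CL ddfm=KENWARDROGER" and an AR(1) structure over visits. Treatment is crossed with time; baseline is not. SAP 6.5 adds only the order in which covariance structures are tried. SAP 3.4 (item 3) records that this MMRM replaces the protocol's multiple-imputation sensitivity analysis.

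SAP 13.2.3 reuses the model: SD-OCT, HVF and contrast sensitivity parameters "will be analyzed separately using a MMRM model, with adjustment for baseline score, as described in section 13.1.6", and VFQ-25 and SF-36 follow the same route. Change in LogMAR at later visits (SAP 13.2.3) and change from nadir (SAP 13.3) are analysed by ANCOVA and are not affected.

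**The concern.** The dependence of change on baseline is unlikely to be the same at Day 1 and at Week 78. The Day 1 measurement comes two or three days after baseline, so change can hardly depend on baseline yet. By Week 78 it may depend on it strongly. Primary eyes may be not yet affected at entry (SAP 3.1), and Protocol 6.1 cites bilateral involvement in more than 97% of subjects at 12 months, so near-normal eyes can lose most of their acuity. Eyes at hand motion, scored 2.3 (SAP 13.1.1), have little room to worsen.

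One slope averaged over such visits is too small for Week 78. The MMRM would then leave part of any chance baseline imbalance uncorrected at the time point that matters. What is at stake is interpretation. The MMRM is there to show whether imputation drives the primary result, and Protocol 10.1 expects less than 5% dropout before Year 1.5. As an illustration, if 5% of one arm were imputed and each value were wrong by 0.3 LogMAR (assumed), the treatment difference would move by 0.05 × 0.3 = 0.015. A slope artefact of similar or larger size would blur that signal.

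**Working it through.** **Inputs from the documents.** Two-sided alpha 0.05; power 80%; "a treatment effect of 0.3 LogMAR in the change from baseline"; "a standard deviation of 0.55 LogMAR has been estimated for the LogMAR change from baseline"; and "this is reduced to 0.50 with the inclusion of baseline LogMAR as a covariate". There are 45 subjects per arm and nine post-treatment visits to Week 78 (Days 1, 14, 28, 56, 84, 168, 252, 365, 548).

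**Assumed, because the documents do not say.** The 0.55 and 0.50 apply at Week 78 (the text speaks of each available visit); the slope-over-time profile; the within-subject correlation rho.

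**1. The plan's own figure.** n = 2 × (1.96 + 0.8416)² × 0.50² / 0.30² = 43.6, so 44 per arm by the normal approximation. The noncentral t gives power 0.795 at 44 and 0.804 at 45. The stated 45 per arm reproduces.

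**2. Implied Week 78 slope.** sqrt(0.55² − 0.50²) = sqrt(0.0525) = 0.229 LogMAR per baseline SD, a correlation of 0.229/0.55 = 0.417 in size.

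**3. Where the gap comes from.** With complete data and treatment crossed with time, each model's Week 78 difference is the raw difference minus slope × baseline imbalance. Therefore

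gap = (Week 78 slope − common slope) × imbalance.

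In simulated complete-data trials, adding `logmar0*time` made the Week 78 MMRM difference equal the ANCOVA estimate to within 1e-14. Without the term the two differed.

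**4. How the common slope is formed.** Under AR(1), the generalised least squares weights on the nine visit slopes are proportional to 1 for the first and last visits and 1 − rho for each of the seven between.

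- rho 0.7: total 2 + 7 × 0.3 = 4.1; Day 1 and Week 78 get 24% each, interior visits 7% each.
- rho 0.9: total 2 + 7 × 0.1 = 2.7; Day 1 and Week 78 get 37% each, interior visits 4% each.

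**5. Fraction f of the Week 78 slope that is recovered** (rho 0.5–0.95):

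| Assumed slope profile | f |
|---|---|
| Linear in days | 0.34–0.46 |
| Square root of days | 0.48–0.51 |
| Early plateau | 0.52–0.58 |
| 30% of full size already at Day 1 | 0.63–0.66 |
| Constant | 1.00 |

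If Day 1 is left out (the adjusted window table in SAP 5.3 starts at Visit 5), f at rho 0.9 is still about 0.46–0.61 for growing slopes.

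**6. Size of the gap.** The imbalance, in SD units, has standard error sqrt(2/45) = 0.211, so the gap SD is (1 − f) × 0.229 × 0.211 = (1 − f) × 0.0483.

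- f = 0.40: SD 0.029; P(gap beyond ±0.03) = P(|Z| > 1.03) ≈ 30%.
- f = 0.65: SD 0.017; P(|Z| > 1.77) ≈ 8%.

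Simulated gap SDs for growing slopes were 0.017–0.030, with a mean gap of about zero. With a constant slope only slope-estimation noise remained (SD about 0.005 at rho 0.9).

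**7. Precision.** The standard error ratio is approximately sqrt(1 + [(1 − f) × 0.229/0.50]²): 1.037 at f = 0.40 and 1.013 at f = 0.65. Simulation with slopes starting near zero gave 2–4%. For scale, the ANCOVA standard error is about 0.105 and the target effect 0.30.

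**The case against.** The case for leaving the model alone is substantial. The effect depends on a slope profile that the documents do not supply. A zero slope at Day 1 ignores regression to the mean: measurement error in baseline acuity alone ties change to baseline at the first visit. A gap SD of 0.026 LogMAR is about 1.3 letters at 0.02 per letter. Randomisation makes the expected gap zero, and SAP 6.3 spends all alpha on the primary analysis. All of this stands and sets the rating.

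Four stronger inferences are tempting, and the documents do not support them.

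- **That this MMRM is the only unimputed look at the primary endpoint.** SAP 13.1.5 repeats the ANCOVA in the PP population, for which SAP 4.4 rules out imputation. PP also removes major deviators and uses treatment received, so it does not isolate imputation, but it exists.
- **That all continuous secondary endpoints are affected.** LogMAR change and change from nadir use ANCOVA. VFQ-25 and SF-36 are first measured after treatment at Week 24 (Protocol 9.2), so the Day 1 argument does not reach them.
- **That not-yet-affected eyes make the slope much steeper, say 0.40 per SD.** With residual SD 0.50, that implies a total SD of sqrt(0.50² + 0.40²) = 0.64, above the plan's 0.55.
- **That adding the term makes MMRM–ANCOVA agreement a clean test of imputation.** AR(1) also imposes one variance on all visits. If the residual SD grew from about 0.17 at Day 1 to 0.50 at Week 78 (assumed), the MMRM standard error was 0.071–0.077 against about 0.106 for the ANCOVA, and 12–17% of simulated trials changed significance. That is a separate cause.

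**Conclusion.** The point holds as a minor one. If the baseline slope grows between Day 1 and Week 78, the common-slope MMRM recovers only about 40–65% of the Week 78 slope and can differ from the primary ANCOVA with no data missing. The gap is zero on average, has SD about 0.017–0.030 LogMAR and exceeds 0.03 in roughly 8–30% of trials. The standard error is about 2–4% larger when the slope starts near zero, and about 1% larger if 30% of it is present at Day 1.

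These figures rest on three assumptions: that the 0.55 to 0.50 reduction describes Week 78, on the assumed profiles, and on AR(1) correlation. If the slope is constant, the systematic gap disappears. Neither the primary test nor its validity is in question. What is lost is some of the diagnostic value of the analysis that replaced multiple imputation, because a gap of a few hundredths of a LogMAR could come from the slope and not from imputation.

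**What to change.** In SAP 13.1.6, add `logmar0*time` to the MMRM model statement, keeping the existing terms. With nine visits this costs up to 8 degrees of freedom and needs no new data. Add the matching baseline-by-time term, using each endpoint's own baseline, to the SD-OCT, HVF and contrast sensitivity MMRMs in SAP 13.2.3; the cost is up to 12 degrees of freedom if Visits 4 to 16 are modelled. For VFQ-25 and SF-36 the term is optional, for consistency. If the 1.5-year analysis has already been run, report the extended model beside it. The AR(1) common variance needs its own decision, for example an unstructured or at least a heterogeneous-variance covariance; this change does not settle it.
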